8. SELECTION AND WITHDRAWAL OF SUBJECTS

8.1. Inclusion Criteria

- 1) If <18 years of age, subject's parent or legal guardian must sign a written informed consent and subject must sign a written informed assent according to the requirements of the site's IRB/EC. If ≥18 years of age, subject must sign a written informed consent according to the requirements of the site's IRB/EC.
- 2) Subjects must be ≥ 6 years of age at time of screening.
- 3) Subjects must weigh at least \geq 18 kg (39.6 lbs.).
- 4) Subjects must have TD based on Diagnostic and Statistical Manual for Mental Disorders 5th Edition (DSM-5-TR diagnostic riteria) for TD.
- 5) Subjects must exhibit both motor and vocal tics that cause impairment with normal routines.
- 6) Subjects must have a minimum score of 20 on the YGTSS-TTS at Screening and at Baseline visits with tic symptoms causing impairment in the subject's normal routines, including academic achievement and/or occupational functioning, and/or social activities, and/or relationships r whose symptoms distress the subject to the extent that treatment is appropriate
- 7) Female participants of childbearing potential must agree to use a highly effective method of contraception (i.e., pregnancy rate of less than 1% per year) during the study and for 30 days after the discontinuation of the IMP. Adequate contraceptive methods include combined hormonal contraception associated with inhibition of ovulation (oral, intravaginal, transdermal), progestogen-only hormonal contraception with inhibition of ovulation (oral, injectable, implantable), intrauterine devices (IUDs), intrauterine h rmone-releasing system (IUS), true sexual abstinence (when this is in line with the preferred and usual lifestyle of the participant), bilateral tubal occlusion, vasectomized male partner, or a female participant who is not of childbearing potential.
 - Female participants and female partners of male study participants using a hormonal contraceptive must also use a barrier method (i.e., condom or occlusive cap [diaphragm or cervical/vault caps]) and should have been stable on their hormonal contraceptive treatment for at least 4 weeks prior to Screening.
- 8) Sexually active male subjects must use a highly effective method of contraception during the study and agree to continue the use of highly effective contraception for at least 30 days after the last dose of study drug.
- 9) For sites in the EU only, the subject must have received an adequate trial of non-pharmacological therapy without adequate response prior to study enrollment.

8.2. Exclusion Criteria

Individuals meeting any of the following criteria at Screening or Baseline are ineligible to participate in the study:

Protocol EBS-101-TD-301 Version 9.0, 05 March 2024

- 1) Subjects with previous exposure to ecopipam (e.g., participated in study PSY301, PSY302 or EBS-101-CL-001).
- 2) Subjects with any unstable mood disorder (DSM-5-TR criteria) at Screening or Baseline.
- 3) Subjects who have unstable medical illness or clinically significant abnormalities on laboratory tests, or ECG at Screening as determined by the Principal Investigator.
- 4) Subjects with a significant risk of attempting suicide based on history (suicide attempt in past 1 year or who have had 2 or more lifetime suicide attempts) or who had an answer of "yes" on any question other than 1–3 (currently or within the past 30 days) on the baseline/screening version of the Columbia Suicide Severity Rating Scale (C-SSRS).
- 5) Subjects with a clinical presentation at Screening or Baseline and/or history consistent with another neurologic condition that may have had accompanying abnormal movements (e.g., Huntington's disease, Parkinson's disease, Wilson's disease, stroke, Restless Legs Syndrome).
- 6) Female subjects who are currently pregnant or lactating or planning to become pregnant during the study.
- 7) Subjects who have moderate to severe renal impairment.
- 8) Subjects who have hepatic impairment at Screening.
- 9) Subjects with current or recent (past 3 months) history of DSM-5-TR substance use disorder (except for nicotine).
- Subjects with positive urine drug screen for cocaine, amphetamine, benzodiazepines, barbiturates, phencyclidine (PCP), or opiates at Screening, except those receiving stable, prescribed treatment for attention deficit/hyperactivity disorder (ADHD).
- 11) Subjects with a ≥25% difference in the absolute change in YGTSS-TTS between the Screening visit and the Baseline visit.
- Subjects with a lifetime history of bipolar disorder type I or II, dementia, schizophrenia, or any other psychotic disorder.
- 13) Subjects with an onset of a major depressive episode in the past 6 months.
- 14) Subjects with a PHQ-9 score of ≥10 at Screening or Baseline.
- Subjects with a history of seizures (excluding febrile seizures that occurred >2 years prior to Screening).
- 16) Subjects with a history of neuroleptic malignant syndrome.
- 17) Subjects with a myocardial infarction within 6 months prior to Screening.
- 18) Subjects who have had previous treatment with:
 - o investigational medication within 4 weeks prior to Screening
 - o oral neuroleptics within 4 weeks prior to Screening
 - o depot neuroleptics within 3 months prior to Screening (e.g., risperidone microspheres) or 6 months prior to screening (e.g., paliperidone palmitate)
- 19) Subjects receiving any other medication to treat motor or vocal tics for at least 14 days prior to Baseline.

Protocol EBS-101-TD-301 Version 9.0, 05 March 2024

- 20) Subjects receiving unstable doses or excluded medications to treat depression, anxiety or ADHD for a minimum of 4 weeks prior to Screening.
- Subjects who have a need for medications which would have unfavorable interactions with ecopipam, e.g., CYP2D6, CYP3A4, CYP2C19, P-gp, substrates with a narrow therapeutic window (e.g., digoxin), inhibitors of CYP2D6 (e.g., fluoxetine), broadspectrum UGT enzyme inhibitors (e.g., valproic acid), dopamine antagonists (e.g., neuroleptics) or agonists (including bupropion), tetrabenazine, VMAT-2 inhibiters (e.g. tetrabenazine), tricyclics and tetracyclics, monoamine oxidase inhibitors, or St. John's Wort. See Section 23.
- 22) Subjects who have initiated new psychological therapies or deep brain stimulation within 10 weeks prior to Baseline visit.
- 23) Initiation or changes in psychological therapies during the study (i.e., Habit Reversal Training or Comprehensive Behavioral Intervention for Tics) as well as deep brain stimulation.
- 24) Subjects unable to swallow tablets.
- 25) Subjects with a known hypersensitivity to any excipients of ecopipam tablets, including subjects with confirmed lactose intolerance.
- 26) Subjects who are employed by the sponsor, vendors working on the study, study site personnel or their family members.
- 27) Siblings or family members of any current subject participating in the study.
- 28) Subjects deprived of liberty by administrative or judicial decision, patients under court protection, guardianship curatorship or family guardianship.
- 29) Any subject who in the opinion of the investigator is not a suitable candidate for the study.

8.3. Subject Withdrawal, Removal, and Replacement Criteria

Any subject with a new positive response on questions 4 and/or 5 of the C-SSRS will be immediately discontinued and evaluated for risk.

Any subject with a CDRS-R or a PHQ-9 assessment indicative of the onset of a new depressive episode at any visit can be discontinued from study participation at the discretion of the Investigator.

Subjects will be discontinued due to attempted suicide or suicidal behavior, oculogyric crisis, neuroleptic malignant syndrome, new onset seizures, serotonergic syndrome, or tardive dyskinesia. Subjects will also be discontinued if there are any adverse events that are Grade 4 (life-threatening consequences; urgent intervention indicated) in severity per CTCAE version 5. The Investigator or subject may choose to stop study treatment at any time for safety or personal reasons. Where possible, a subject who discontinues treatment will undergo protocol-specified end-of study procedures at the time of discontinuation. Date and reason(s) of premature discontinuation will be described in the CRF.

Subjects who discontinue treatment for any reason, other than an SAE (even if the SAE is not treatment related) or an AE (unless the AE can be determined to be unrelated to treatment), may be replaced only after consultation with Sponsor or its representative.

9. TREATMENT OF SUBJECTS

9.1. Description of Study Drug

Table 4: Investigational Product

| | Investigational | product |
|------------------------------|--|--|
| Product Name | Ecopipam | Placebo |
| Dosage Form | Tablets | Matching tablets |
| Unit Dose of Ecopipam | 11.2, 22.4, 33.6, 44.8, 67.2 and 89.6 mg | Matahing unit daga tahlata |
| Unit Dose of Ecopipam HCl | 12.5, 25, 37.5, 50, 75 and 100 mg | Matching unit dose tablets |
| Route of Administration | Oral | Oral |
| Physical Description | Round, biconvex, light blue film-coated tablet, plain on both side | Round, biconvex, light blue film-coated tablet, plain on both side |
| Manufacturer | Catalent Pharma Solutions, LLC | Catalent Pharma Solutions, LLC |

9.2. Concomitant Medications

For subjects who receive study treatment, any medication (including over-the-counter medications) administered to the subject during the study (starting at the date of informed consent) will be recorded on the Prior and Concomitant Medication CRF. Nonpharmacologic therapies/procedures will also be captured on the CRF. The Investigator will record any AE on the Adverse Events CRF for which the concomitant medication was administered.

9.2.1. Allowable Medications for Common Comorbid Conditions

The following medications are allowed for the treatment of subjects with ADHD, anxiety, depression, mood disorder, and OCD if doses have been stable for at least 4 weeks prior to Screening and the dose is not expected to change and remains stable during the course of the study.

Allowable stimulants for comorbid ADHD

- Amphetamine
- Dextroamphetamine
- Amphetamine and dextroamphetamine (mixed salts)

- Dexamphetamine
- Dexmethylphenidate
- Lisdexamfetamine
- Methylphenidate

Allowable medications for anxiety, mood disorders, depression and OCD

- citalopram
- desvenlafaxine
- escitalopram
- fluvoxamine
- levomilnacipran
- milnacipran
- sertraline

Anxiolytics

- lorazepam Chronic use only
- hydroxyzine

9.3. Prohibited Therapies

Since ecopipam and its metabolite (EBS-101-40853) may inhibit CYP2D6, OATP1B1, P-gp and UGT1A9 and induce CYP3A4 and CYP2C19, for any drug that is a substrate of these enzymes, the label for the drug should be co-sulted to decide if a dose adjustment is needed.

Prohibited therapies per the exclusion criteria (Section 8.2) include:

- Previous treatment with ecopipam
- Any investigational medication within 1 month prior to Screening
- Oral neuroleptics within 4 weeks prior to Screening
- Depot neuroleptics within 3 months prior to Screening (e.g., risperidone microspheres) or 6 months prior to screening (e.g., paliperidone palmitate)
- Any medications for the treatment of tics for at least 14 days prior to Baseline
- Subjects receiving unstable doses or excluded medications to treat depression, anxiety or ADHD for a minimum of 4 weeks prior to Screening.
- Subjects who have a need for medications which would have unfavorable interactions with ecopipam, e.g., CYP2D6, CYP3A4, CYP2C19, P-gp, substrates with a narrow therapeutic window (e.g., digoxin), inhibitors of CYP2D6 (e.g., fluoxetine), broadspectrum UGT enzyme inhibitors (e.g., valproic acid), dopamine antagonists (e.g.,

| Emalex Biosciences, | Inc. |
|---------------------|------|
| Ecopipam | |

Protocol EBS-101-TD-301 Version 9.0, 05 March 2024

neuroleptics) or agonists (including bupropion), tetrabenazine, VMAT-2 inhibiters (e.g. tetrabenazine), tricyclics and tetracyclics, monoamine oxidase inhibitors, or St. John's Wort. See Section 23.

- New psychological therapies that were initiated within 10 weeks prior to the Baseline visit
- Initiation or changes in psychological therapies during the study (i.e., Habit Reversal Training or Comprehensive Behavioral Intervention for Tics) as well as deep brain stimulation.

An illustrative, but not complete, list of excluded drugs is provided in the Prohibited Medications List in Section 23.

9.4. Treatment Compliance

During the study period, subject compliance will be monitored by review of the unused tablet counts at the study site visits. Less than 80% compliance will require evaluation by the Investigator and Sponsor or its representative to determine if the subject may continue the study.

9.5. Randomization and Blinding

Randomization will be stratified by weight band Throughout the study, subjects, caregivers, and all personnel involved with the conduct and interpretation of the study, including the investigators, site personnel, and sponsor staff will be blinded to the treatment codes. Randomization data will be kept strictly confidential, filed securely by an appropriate group with the Sponsor or CRO and accessible only to authorized persons (e.g., Safety) until the time of unblinding.

A master list of all treatments and the subject numbers associated with them will be maintained electronically in the Interactive Web Randomization System (IWRS). The process to request a randomization code will be outlined in the IWRS user manual. The site will be trained in this process and should only be used in an emergency. These codes should only be broken if knowledge of the subject's randomization code will affect his/her medical treatment. If necessary, the Investigator may consult with the sponsor before breaking the blind. The Investigator is to record the date and time of requesting the code and the reason for breaking the code.

Protocol EBS-101-TD-301 Version 9.0, 05 March 2024

10. STUDY DRUG MATERIALS AND MANAGEMENT

10.1. Study Drug

Ecopipam tablets and matching placebo tablets.

10.2. Study Drug Packaging and Labeling

Study drug will be supplied in labeled containers by the Sponsor. The product release certificates for ecopipam tablets will be included in the clinical study report for this protocol. Any special storage conditions will be noted on the label and should be followed by the study site.

The labels will be produced by PCI Pharma Services. Minimally, the labels will contain the following information. This will be adapted for any local laws and regulations:

- 1. Name, address, and telephone number of the Sponsor
- 2. Pharmaceutical dosage form, route of administration, quantity of dosage units, identifier, and dose strength
- 3. Lot number
- 4. Protocol Number
- 5. Study subject identification number
- 6. Directions of use
- 7. "Caution: New Drug Limited by Federal (US) law to investigational use" (or equivalent for rest of world)
- 8. Storage Conditions
- 9. Expiration Date

10.3. Study Drug Storage

Study drug is to be stored at 59°F to 77°F (15°C to 25°C) protected from light, excessive heat, open flame and combustibles, out of direct sunlight, and in a well-ventilated, dry area.

All relevant site-specific guidelines and country-specific labeling requirements must be followed. Study drug must be kept in a secure location and carefully stored at the study site within its original container. A daily temperature log for monitoring of proper storage conditions must be maintained by the site.

10.4. Study Drug Preparation

Study drug primary packaging will be in blister packs for ecopipam and matching placebo. No preparation is required.

Protocol EBS-101-TD-301 Version 9.0, 05 March 2024

10.5. Administration

During the 4-week titration phase of the open-label Stabilization period, the following ecopipam doses will be administered PO for each of the weight bands (see Table 5):

Table 5: Proposed Dosing Regimen

| Weight (kg) | Wee | ek 1 | Week 2 | | We | ek 3 | Week 4 | | |
|-------------|--------------------|---------------------------|--------------------|---------------------------|--------------------|---------------------------|--------------------|---------------------------|--|
| | ecopipam mg/day | ecopipam HCl mg/day | ecopipam mg/day | ecopipam HCl mg/day | ecopipam mg/day | ecopipam HCl mg/day | ecopipam mg/day | ecopipam HCl mg/day | |
| ≥18 - ≤23 | 11.2 | 12.5 | 22.4 | 25 | 33.6 | 37.5 | 33.6 | 37.5 | |
| >23 - ≤34 | 11.2 | 12.5 | 22.4 | 25 | 33.6 | 37.5 | 44.8 | 50 | |
| >34 - ≤44 | 11.2 | 12.5 | 22.4 | 25 | 44.8 | 50 | 67.2 | 75 | |
| >44 - ≤68 | 22.4 | 25 | 44.8 | 50 | 67.2 | 75 | 89.6 | 100 | |
| >68 - ≤83 | 22.4 | 25 | 44.8 | 50 | 89.6 | 100 | 134.41 | 150¹ | |
| >83 | 22.4 | 25 | 44.8 | 50 | 89.6 | 100 | 179.2 ² | 200^{2} | |

¹ 134.4 mg ecopipam dose (150 mg ecopipam HCl) given as two tablets containing 67.2 mg ecopipam (75 mg ecopipam HCl) each.

Subjects who do not tolerate the dose titration up to the full designated dose for their weight stratum will be discontinued from the study. These subjects will be tapered off their current dose of study drug according to their weight stratum.

During Weeks 4 to 12 of the open-label maintenance phase and for Responders in this period who are randomized to ecopipam for the 12-week R/WD period, the following ecopipam HCl doses will be administered f r each of he weight bands:

- Those who weigh $\ge 18 \le 23$ kg will receive 33.6 mg (37.5 mg ecopipam HCl) daily.
- Those who weigh >23 <34 will receive 44.8 mg (50 mg ecopipam HCl) daily.
- Those who weigh >34 \(\le 44 \) will receive 67.2 mg (75 mg ecopipam HCl) daily.
- Those who weigh >44 ≤68 kg will receive 89.6 mg (100 mg ecopipam HCl) daily.
- Those who weigh >68 \le 83 kg will receive 134.4 mg (150 mg ecopipam HCl) daily.
- Those who weigh >83 kg will receive 179.2 mg (200 mg ecopipam HCl) daily.

All doses will be administered PO once daily in the evening without regard to food. Subjects who have changes in weight during the study will not have their doses adjusted for the duration of the study.

Responders who are randomized to placebo for the 12-week R/WD period will taper off ecopipam in decrements by 22.4 mg/day (25 mg/day ecopipam HCl) until off study drug. For the remainder of the R/WD period, these patients will receive matching placebo tablets.

Any subject randomized to placebo who meets Relapse criteria during the R/WD period, or who discontinues the study prematurely due to any reason, will receive a taper kit of matching

² 179.2 mg ecopipam dose (200 mg ecopipam HCl) given as two tablets containing 89.6 mg ecopipam (100 mg ecopipam HCl) each.

| Emalex Biosciences, | Inc. |
|---------------------|------|
| Ecopipam | |

Protocol EBS-101-TD-301 Version 9.0, 05 March 2024

placebo with the same number of tablets as subjects in the same weight band receiving blinded ecopipam to preserve the blind. All subjects will be monitored for signs or symptoms of withdrawal, abuse and dependence.

Non-responders to ecopipam during the Stabilization period, or Responders randomized to ecopipam who complete the R/WD period, or who meets Relapse criteria during the R/WD period, or who discontinues the study prematurely due to any reason will be tapered off ecopipam in decrements of 22.4 mg/day (25 mg/day ecopipam HCl) until off drug. All subjects will be monitored for signs or symptoms of withdrawal, abuse and dependence.

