- Those who weigh $>68 \le 83$ kg will receive 134.4 mg (150 mg ecopipam HCl) daily.
- Those who weigh >83 kg will receive 179.2 mg (200 mg ecopipam HCl) daily.

All doses will be administered once daily in the evening without regard to meals.

Non-responders to ecopipam during the open-label Stabilization period, subjects randomized to placebo during the R/WD period, responders to ecopipam who complete the R/WD period, any subject who meets Relapse criteria during the R/WD period, and any subject who discontinues the study prematurely due to any reason will be tapered off ecopipam in decrements of 22.4 mg/day (25 mg ecopipam HCl) until off drug; signs or symptoms of wi hdrawal, abuse and dependence will be monitored. Subjects assigned to placebo will receive placebo taper down medication to preserve the blind.

Duration of treatment:

Eligible subjects will receive open-label ecopipam tablets for up to 12 weeks. Subjects who qualify as Responders will be randomized at Week 12 to receive either ecopipam tablets or matching placebo for up to 12 weeks for a total of up to 24 weeks of treatment.

Reference therapy, dosage, and mode of administration:

Placebo-controlled, matching placebo tabl ts given by mouth (PO) in the evening.

Criteria for evaluation:

Efficacy:

Confidential

Primary Efficacy Endpoint:

• Time from Randomization (Week 12) to Relapse in subjects ≥ 6 and < 18 years for ecopipam compared to placebo during the double-blind, R/WD period.

Secondary Efficacy Endpoint:

• Time from Randomization (Week 12) to Relapse in all subjects irrespective of age for ecopipam compared to placebo during the double-blind R/WD period.

Exploratory Efficacy Endpoints:

- Time from Randomization (Week 12) to a worsening by at least one category of the CGI-TS-S in subjects ≥6 and < 18 years for ecopipam compared to placebo during the double-blind R/WD period. If there is a strong correlation of this endpoint with Relapse criteria based on the YGTSS-TTS, it may be considered as a secondary endpoint with agreement from Health Authorities.
- Time from Randomization (Week 12) to a worsening by at least one category of the CGI-TS-S in all subjects for ecopipam compared to placebo irrespective of age. If there is a strong correlation of this endpoint with Relapse criteria based on the YGTSS-TTS, it may be considered as a secondary endpoint with agreement from Health Authorities.

Protocol EBS-101-TD-301 Version 9.0, 05 March 2024

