7. INVESTIGATIONAL PLAN

7.1. Overall Study Design

This is a multicenter study which includes an open-label period followed by double-blind, placebo-controlled, randomized withdrawal period in children (≥ 6 and ≤ 12 years of age), adolescents (≥ 12 and ≤ 18 years of age), and adult subjects (≥ 18 years of age) with TD.

After providing informed consent (adult subjects or caregivers to children/adolescents) and assent (children/adolescents) and following an up to 28-day Screening period, and with agreement by Eligibility Review by the study team, subjects will proceed to the Baseline visit (Day 1).

Eligibility Review is an evaluation and quality oversight process of subject eligibility. Sites will complete an Eligibility Review packet at Screening which includes key medical information (e.g., laboratory results, ECG, medical history, physical examination, concomitant medications), scales data (e.g., subject questionnaire responses), and any other information necessary to establish subject eligibility per protocol. A decision to enroll a subject will be made by the investigator only after the Eligibility Review is concluded. The investigator remains responsible for ensuring that subjects are eligible for enrollment.

At the Baseline visit, eligible subjects will be entered into an open-label Stabilization period and start a 4-week Titration phase to achieve a target steady-state dose of 1.8 mg/kg/day ecopipam (2 mg/kg/day ecopipam HCl) followed by an 8 week open-label maintenance phase.

During the open-label Stabilization period, subjects will return to the clinic at Baseline (Day 1) and Weeks 4, 8 and 12. Subjects will have a telephone visit at Week 2 to assess adverse events (AEs) and other safety parameters. Efficacy assessments will be conducted at Weeks 4, 8 and 12. PK samples will be collected at Weeks 4 and 8. A PK assessment may be collected at Week 12 if the Week 8 PK assessment is missed. Safety assessments will be conducted at all visits.

Responders to ecopipam, defined a those with ≥ 25% improvement from Baseline (Day 1) on the YGTSS-TTS at both Weeks 8 & 12 during the open-label Stabilization period, will be randomized to ecopipam 1.8 mg/kg/day (ecopipam HCl 2 mg/kg/day) or placebo in a 1:1 fashion and enter a double-blind Randomized-Withdrawal (R/WD) period at Week 12. Subjects randomized to placebo will be tapered off ecopipam in a blinded fashion in decrements of 22.4 mg/day (25 mg/day ecopipam HCl).

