Responders who are randomized to placebo for the 12-week R/WD period, will taper off ecopipam in decrements by 22.4 mg/day (25 mg/day ecopipam HCl) until off study drug. For the remainder of the R/WD period, these patients will receive matching placebo tablets. Any subject randomized to placebo who meets Relapse criteria during the R/WD period, or who discontinues the study prematurely due to any reason will receive a taper kit of matching placebo with the same number of tablets as subjects in same weight band receiving blinded ecopipam to preserve the blind. All subjects will be monitored for signs or symptoms of withdrawal, abuse, and dependence.

Non-responders to ecopipam during the Stabilization period, or Responders randomized to ecopipam who complete the R/WD period, or who meet Relapse criteria during the R/WD period, or who discontinue the study prematurely due to any reason will be tapered off ecopipam in decrements of 22.4 mg/day (25 mg/day ecopipam HCI) until off drug. All subjects will be monitored for signs or symptoms of withdrawal, abuse and dependence.

<sup>2 179.2 mg ecopipam dose (200 mg ecopipam HCl) given as two tablets containing 89.6 mg ecopipam (100 mg ecopipam HCl) each.

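### The placebo-only taper kit in Protocol 10.5 and SAP 4.5 makes no exception for placebo-arm subjects who exit while still on the blinded ecopipam taper, and the synopsis states both rules without settling that case

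*Protocol*

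**What the plan says.** **Placebo-arm subjects are on active drug after randomization.** Protocol 7.1: "Subjects randomized to placebo will be tapered off ecopipam in a blinded fashion in decrements of 22.4 mg/day". Protocol 10.5 agrees: "Responders who are randomized to placebo for the 12-week R/WD period will taper off ecopipam in decrements by 22.4 mg/day". Placebo alone comes only afterwards: "For the remainder of the R/WD period, these patients will receive matching placebo tablets".

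**The exit kit follows the randomized arm.** The next paragraph of Protocol 10.5 applies to "Any subject randomized to placebo who meets Relapse criteria during the R/WD period, or who discontinues the study prematurely". The reason for leaving does not matter, and the kit holds no active drug; its content is "placebo with the same number of tablets as subjects in the same weight band receiving blinded ecopipam to preserve the blind". SAP 4.5 has the same rule: such a subject "will receive a taper kit of matching placebo with the same number of tablets as subjects in same weight band".

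**The synopsis states a stepwise taper, then a placebo taper.** Under the investigational product heading, one sentence lists subjects randomized to placebo, subjects who meet Relapse criteria and others, and ends: "any subject who discontinues the study prematurely due to any reason will be tapered off ecopipam in decrements of 22.4 mg/day". The paragraph closes by giving placebo-assigned subjects placebo taper medication to keep the blind. The synopsis Methodology text and SAP 4.1 likewise pair a taper for anyone who discontinues with a placebo-taper sentence.

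**Who gets the active exit taper.** The last paragraph of Protocol 10.5, and the matching paragraph of 7.1, name non-responders and Responders randomized to ecopipam. They do not name placebo-arm subjects.

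No passage in either document says how long each decrement lasts, or what a placebo-arm subject who exits before the blinded taper ends should receive.

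**The concern.** The kit rule depends on the arm, not on what the subject is taking that day. Early in the randomized-withdrawal period the two differ, because a placebo-arm subject may still be taking a substantial ecopipam dose. If that subject relapses or leaves, the kit rule replaces whatever remains with placebo in one move, while the synopsis sentence calls for decrements of 22.4 mg/day until off drug. Both cannot be followed for the same person.

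The case can arise in practice. Relapse is assessed weekly at Weeks 13 to 16, when a taper may still be running. Table 3 has unused drug collected and new drug dispensed at the Week 24/Relapse/ET visit, so the kit determines what is taken next. Elsewhere Protocol 10.5 does write a rule based on the current dose, for subjects who cannot tolerate titration. The lack of one here is therefore a gap that a reader cannot fill by analogy.

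At stake is the consistency of a dosing instruction for children, adolescents and adults. A smaller matter is whether adverse events after such an exit can be recognised in the down-titration summaries, which SAP 12 presents by treatment group.

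**Working it through.** **Is the conflict in the text?** Take a placebo-arm subject who exits mid-taper.

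- Synopsis, investigational product: the subject is named in the list of those tapered in decrements until off drug.
- Same paragraph, last sentence: the subject is assigned to placebo, so receives placebo taper medication.
- Protocol 10.5 and SAP 4.5: the subject receives a placebo-only kit, whatever dose remains.
- Last paragraph of Protocol 10.5, and Protocol 7.1: the subject is not among those given an active exit taper.

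The outcomes differ, and no passage ranks one above another. This does not depend on the step length.

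**Which subjects are affected?** Maintenance doses are those listed below Table 5. Subtract 22.4 mg/day until zero. A move from 22.4 mg/day or less to zero is a single permitted decrement, so the conflict matters only while more than 22.4 mg/day remains. Let k be the number of dose levels above 22.4 mg/day after the first cut, with the first reduced dose assumed to be taken on the first day of the period.

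**How likely is Relapse in that interval?** The plan gives no figure, so this is an illustration. With the planned 65% placebo Relapse over 12 weeks as a constant hazard:

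h = -ln(1 - 0.65)/12 = 0.0875 per week.

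P = 1 - exp(-h × k × L), where L is the assumed step length in weeks (1 for weekly steps, 1/7 for daily steps).

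| Weight (kg) | Dose (mg/day) | Decrements to zero | Left after first cut (mg/day) | k | P, weekly steps | P, daily steps |
|---|---|---|---|---|---|---|
| 18-23 | 33.6 | 2 | 11.2 | 0 | 0% | 0% |
| >23-34 | 44.8 | 2 | 22.4 | 0 | 0% | 0% |
| >34-44 | 67.2 | 3 | 44.8 | 1 | 8.4% | 1.2% |
| >44-68 | 89.6 | 4 | 67.2 | 2 | 16.1% | 2.5% |
| >68-83 | 134.4 | 6 | 112.0 | 4 | 29.5% | 4.9% |
| >83 | 179.2 | 8 | 156.8 | 6 | 40.8% | 7.2% |

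Example, above 83 kg: weekly steps give 1 - exp(-0.0875 × 6) = 40.8%; daily steps give 1 - exp(-0.0875 × 6/7) = 7.2%.

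**Effect of the visit schedule.** Relapse on the YGTSS-TTS is scored only at visits, the first nominally seven days after randomization. With daily steps, every band is at zero by day 7 except the heaviest, where 179.2 - 7 × 22.4 = 22.4 mg/day remains, which is one decrement. Scored Relapse at the nominal Week 13 visit would then cause no breach. A visit three days early, still inside the window, would find 134.4 - 4 × 22.4 = 44.8 mg/day in the >68-83 kg band and 179.2 - 4 × 22.4 = 89.6 mg/day above 83 kg. With weekly steps, every band is still on drug at Week 13 (11.2 to 156.8 mg/day), and the heaviest band's last active day is (8 - 1) × 7 = day 49.

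**The case against.** The strongest reply is that this is an unaddressed edge case and not two opposed instructions. The kit rule in Protocol 10.5 follows directly after the sentence about placebo for the rest of the period, so it can be read as a dummy taper for subjects already on placebo. The synopsis has the same structure, a general taper followed by a placebo-arm provision. Sites are blinded and work through the IWRS, whose kit logic is not visible in the documents and may already handle the case.

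The calendar also hints at a short taper. Table 3 places follow-up at Days 170 to 199 although those visits are counted from the last dose, its footnote foresees extension entry within 30 days of Week 24, and the SAP adverse-event windows end at Day 184. If the last dose includes the exit taper, weekly steps fit poorly. This is indirect evidence, but it argues against the larger percentages.

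Much of this stands as a limit on size. It does not remove the conflict. The kit rule covers any placebo-arm subject at any time in the period, the synopsis list names placebo-arm subjects, and nothing says which governs mid-taper.

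A reader might also infer three stronger points that the documents do not support:

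- **That everyone leaving mid-taper is stopped against the taper rule.** Subjects with 22.4 mg/day or less left are one permitted decrement from zero. In the two lightest bands that is everyone past the first cut.
- **That Protocol 7.1 contradicts 10.5 on who gets the active exit taper.** The two agree; the tension is with the synopsis and SAP 4.1.
- **That the withdrawal-safety comparison is distorted.** The SAP summarizes safety by actual treatment, with time windows and separate Weeks 13-16, Weeks 17-24 and down-titration periods. Such subjects could be pooled in the down-titration table, but neither their number nor any effect is shown. Protocol 5.2.2 reports no withdrawal signs in the earlier phase 2b study, so no harm is asserted here.

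**Conclusion.** The conflict holds in a bounded form. Protocol 10.5 and SAP 4.5 give a placebo-only kit to any placebo-arm subject who relapses or discontinues, while the synopsis and SAP 4.1 carry both a stepwise taper and a placebo taper and leave the mid-taper case open. Followed literally, the kit rule removes more than one decrement at once for subjects above 34 kg who exit with more than 22.4 mg/day left. Above 83 kg, up to 156.8 mg/day, or seven decrements, would be replaced at once.

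How many subjects this would affect cannot be computed, because the step length is missing. The illustrative range is 0, 0, 8, 16, 30 and 41% of placebo-arm subjects by weight band with weekly steps, and about 0-7% with daily steps. It assumes a constant hazard and a first cut on the first day. These are upper figures for Relapse, because hazard is probably lower while drug remains and YGTSS-TTS Relapse is detected only at visits. With daily steps the figure at the nominal Week 13 visit is about zero. Exits for other reasons are not counted.

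A reader might instead count every step on drug, including the last, and reach 8-46% with weekly steps. That includes subjects for whom going to zero is already a permitted decrement.

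The point should be corrected because it concerns a dosing instruction and is cheap to settle, not because a large effect on the trial has been shown.

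**What to change.** Reconcile the synopsis (Methodology and investigational product text), Protocol 7.1 and 10.5, and SAP 4.1 and 4.5, so that one explicit rule covers placebo-arm subjects who relapse or discontinue before the blinded ecopipam taper has ended. Which rule applies is the sponsor's clinical decision, and none is proposed here. State the time per decrement in the protocol. Confirm that the IWRS kit assignment follows the chosen rule.

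Optionally, identify these subjects by date of last active dose in the down-titration adverse-event listing, so that they can be told apart from placebo subjects who had finished the taper.

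The cost is wording in two documents and a check of the kit logic, plus one listing variable if the option is taken. No visits or subjects are added.
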